9. MEDICARE AND MEDICAID CLAIMS DATA COLLECTION AND ANALYSIS

9.1 Rationale

The economic analyses will be conducted from the perspective of the payer with the primary goal to provide cost-effectiveness data that can inform reimbursement decisions for genotyping. Reporting metrics will include:

1. Average costs for each study arm, considering overall cost to the payer and select services directly relevant to the acute pain, chronic pain, and depression groups
2. Differences in cost utility between the intervention arm, considering overall cost to the payer and select services directly relevant to the acute pain, chronic pain, and depression groups
3. Incremental cost-effectiveness ratio (ICER), i.e., the incremental change in cost per unit improvement of effectiveness.

All metrics will be ascertained over a 6-month follow-up period with the assumption that beneficial effects of genotype-guided therapy are fully realized within this time period and that the control arm participants have not yet developed any cross-over effects from the 6-month delayed testing.

In a population of mixed payer types, collecting actual costs for all participants is not feasible. Therefore, costs will be obtained from Medicare and Medicaid claims data and imputed or cross-walked to the other payer types. Based on data in the National Inpatient Sample, 53% and 4% of knee and 59% and 4% of hip arthroplasties were reimbursed by Medicare and Medicaid, respectively. For chronic pain participants, data from the University of Florida suggest 40% and 20% are covered by Medicare and Medicaid, respectively. Thus, considering enrollment gaps, at least 60% of the study population is anticipated to have claims data, from which comprehensive cost analyses can be performed and extrapolated to the entire cohort. Major cost drivers associated with pain and depression will be ascertained from the participant using validated resource questionnaires, and verified through secondary claims data whenever possible.

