reasons, we will conduct covariate-adjusted repeated measures mixed models that will account for differences in baseline characteristics that differ between the Intervention – CYP2D6 PM or UM or CYP2C19 UM, RM or PM subgroup and the Control – CYP2D6 PM or UM or CYP2C19 UM, RM or PM subgroup. Potential baseline characteristics may include age, sex, income, education, insurance, medical conditions. We will select the appropriate covariance matrix (e.g. compound symmetry, autoregressive, unstructured, or other covariance structure) based on the data.

Difference within the NM group. In the control arm participants, we will compare depression scores and depression control in participants with a CYP2D6 activity score $>0.75 - 1$ to participants with an activity scores $>1-2$ using a two-sided two-sample t-test or Mann Whitney test, as appropriate, with a type 1 error of 0.05. Additionally, we will use linear regression to adjust for differences in baseline characteristics

Cost Effectiveness

Healthcare costs: In the Medicare fee-for-service or Medicaid enrollees, log-transformed overall expenditures (between index visit and 6 months follow-up) will be compared using a 2-sample t-test between the study arms (after ensuring that the variances in the log-scale are equal). Alternatively, cost comparisons will be made using appropriate regression models such as generalized linear models. For all participants, regardless of insurance type, we will estimate and aggregate participant-reported healthcare utilization during follow-up and assign cost for each item based on unit weighted mean cost estimates from the Medicare/ Medicaid data.

Within the Medicare/Medicaid population, we will compare estimated cost differences between genotype-guided and usual care based on billing records versus participant report to further validate the cost comparisons for the entire population. Cost for the index hospitalization for surgery participants will not be included in the cost estimate, but we will compare length of stay between groups as reference for hospitals regarding potential cost savings in capitation-based reimbursement schemes. All costs will be converted to 2021 \$US using the chain-weighted Consumer Price Index (CPI).

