Finally, we will compare the Medicare/Medicaid beneficiaries among our trial enrollees to a larger random sample of beneficiaries in the participating states and compare demographic and key clinical characteristics to explore representativeness of our study sample, evaluate the impact of attrition and loss to follow-up and make inferences about the generalizability of our results.

Cost utility: For the cost-utility analysis, the PROMIS-43 responses will be converted into utilities using previously validated crosswalks.[41] Cost and quality adjusted life year (QALY) estimates, adjusted for clustering within site and baseline utility for QALYs, will be obtained using appropriate regression models such as generalized linear models. The analysis of maximum likelihood parameter estimates will allow us to capture differences in cost and QALYs between the intervention arm and control arm of the trial. The Incremental cost-effectiveness ratio (ICER) will be calculated from costs and QALY. A bootstrapping approach will be used to characterize sampling uncertainty and calculate confidence intervals (CI) around the ICER estimate (2.5th and 97.5th percentiles corresponding to the lower and upper bounds of the CI, respectively). This sampling uncertainty will be summarized using cost-effectiveness acceptability curves.

Details of these statistical analyses, along with other exploratory analyses will be described in the study SAP.

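### The first-named cost comparison, a t-test on log expenditures, tests geometric means and has no rule for zero costs, whereas the stated payer metric is average cost per arm

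*Combined protocol and SAP*

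**What the plan says.** Section 9.1 sets the economic analysis from the payer's perspective, to inform reimbursement. Its first reporting metric is "Average costs for each study arm, considering overall cost to the payer", and a later one is the ICER.

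Section 10.6 (Cost Effectiveness, healthcare costs) limits the comparison to people enrolled in Medicaid or in fee-for-service Medicare and states it as follows: "log-transformed overall expenditures (between index visit and 6 months follow-up) will be compared using a 2-sample t-test between the study arms". A condition is attached: "after ensuring that the variances in the log-scale are equal". A second route follows: "Alternatively, cost comparisons will be made using appropriate regression models such as generalized linear models". The section does not say when the second route applies, which family or link it would use, how zero expenditures enter the log, or how a log-scale result becomes a mean cost.

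The cost-utility paragraph of the same section is separate. Its cost and QALY estimates, adjusted for clustering within site, "will be obtained using appropriate regression models such as generalized linear models". Then: "The Incremental cost-effectiveness ratio (ICER) will be calculated from costs and QALY", with bootstrap intervals. Further detail is left to a study SAP, which section 10.2 describes as a separate document for each trial.

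**The concern.** A payer's outlay is the arithmetic mean cost times the number of people covered. A t-test on log cost answers a different question: whether the geometric means differ. If the spread of log costs differs between arms, mean costs can differ while the log test has nothing to find, or be equal while the log test rejects. Participants with no expenditure in the 6-month window cannot be logged at all. Section 10.6 leaves the index surgical admission out of the cost estimate, so zeros are possible in Acute Pain.

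At stake is a standalone cost p-value that disagrees with the mean costs and the ICER reported beside it, with no rule in the plan for which one answers the payer's question.

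**Working it through.** The documents give no mean, SD, zero proportion or power for costs, so there is no cost figure to reproduce. The log-SDs, mean log cost and zero proportions below are assumptions.

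**Inputs from the plan.** Test and equal-variance condition: section 10.6. Metric: section 9.1. Two-sided alpha 0.05: section 10.2. Sample size for illustration: Chronic Pain, 994 randomized (section 10.1), with at least 60% expected to have claims (section 9.1), so 994 × 0.60 / 2 = 298, about 300 per arm. For the 268 with an actionable phenotype, 268 × 0.60 / 2 = 80 per arm.

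**1. What the test targets.** For log-normal costs the geometric mean is exp(μ) and the arithmetic mean is exp(μ + s²/2). Hence

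arithmetic-mean ratio = geometric-mean ratio × exp((s₁² − s₀²)/2).

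The ratios coincide if s₁ = s₀. If geometric means are equal but log-SDs are not:
- 1.4 vs 1.5: exp((1.96 − 2.25)/2) = exp(−0.145) = 0.865, a mean about 13% lower.
- 1.3 vs 1.5: exp((1.69 − 2.25)/2) = exp(−0.28) = 0.756, a mean about 24% lower.

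In both cases the null hypothesis of the log t-test is true.

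**2. Can a check secure equal variances?** The plan names no test; suppose a 5% two-sided test with 300 per arm. The log variance ratio is 2·ln(s₁/s₀), with SE √(4/299) = 0.116.
- 1.4 vs 1.5: 0.138 / 0.116 = 1.19, power about 22%.
- 1.3 vs 1.5: 0.286 / 0.116 = 2.47, power about 70%.

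**3. The opposite error.** Simulation (3,000 runs per row) with equal arithmetic means, log-normal costs and an F-test for the variances:

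| Per arm | Log-SDs | Log t-test rejects | F-test detects | Rejects and passes F-test |
|---|---|---|---|---|
| 298 | 1.3, 1.3 | 5.5% | 4.8% | 5.0% |
| 298 | 1.3, 1.4 | 24.6% | 24.2% | 18.4% |
| 298 | 1.3, 1.5 | 67.8% | 69.8% | 20.8% |
| 80 | 1.3, 1.5 | 23.5% | 24.0% | 18.2% |

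With equal spread the test holds its level. With unequal spread the check removes some false findings about mean cost, but not all.

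**4. Zeros.** Suppose 5% vs 10% have zero cost and positive costs are identically distributed. The mean ratio is 0.90 / 0.95 = 0.947, which a log test on positive costs cannot see. If a constant c is added instead and mean log cost is 8, the 5-point difference shifts the log mean by roughly 0.05 × (8 − ln c). That is 0.40 for $1 (apparent ratio 0.67) and 0.17 for $100 (apparent ratio 0.84). The answer depends on a choice that the plan does not state.

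**The case against.** The strongest reply has five parts.

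- **The ICER does not use this test.** This stands. A reader might infer from section 10.6 that the ICER inherits geometric means, but the cost-utility paragraph takes its costs from regression such as a GLM. Nor does anything say that the average costs in section 9.1 will be derived from log means; they can be reported whichever test is run.
- **The equal-variance condition is the right one.** Under log-normality it makes the two ratios equal, and a check is not powerless: about 70% for 1.3 vs 1.5 at 300 per arm. So a claim that it would miss every difference of importance is not supported. What remains is that smaller differences usually pass, that 80 per arm gives only 24% even for 1.3 vs 1.5, and that the plan states no test, threshold or check of log-normality.
- **Zero costs may be rare.** The enrollees are under treatment and their prescriptions and visits count. The documents give no frequency, so a reading that zeros are common is unsupported. The missing rule is a gap either way.
- **The GLM is already named, and listing it as an alternative need not rank it second.** True, but two methods with different targets and no trigger leave the choice open until the data are seen.
- **Detail is deferred and the analysis is exploratory.** The separate SAP may settle this and cannot be seen here. The synopsis labels the cost-effectiveness work exploratory, and section 3.2 lists no cost endpoint. This limits the priority.

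**Conclusion.** The point holds for the standalone cost comparison. Its first-named test addresses geometric means while section 9.1 asks for average cost per arm, and zeros have no rule. The equal-variance condition narrows the gap without closing it. Under the assumed log-SDs, mean costs can differ by 13% to 24% with nothing for the log test to find; with equal mean costs, about 298 per arm and log-SDs of 1.3 and 1.4, the test rejects in about 25% of trials, and 18% both reject and pass the variance check. These sizes rest on log-normal costs, the assumed spreads, and a 5% variance test that the plan does not name.

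The ICER and the primary and secondary endpoints are unaffected. Priority is low to moderate.

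**What to change.** In section 10.6, make the between-arm difference in arithmetic mean 6-month cost per participant the main cost comparison, with zero-cost participants included. Estimate it with a GLM fitted by quasi-likelihood, or with a two-part model, with robust or bootstrap intervals and adjustment for site. Prior-year claims cost is an optional covariate; sections 7.9 and 9.2 already collect it. State the family or variance function and the link, which the plan does not yet do. Quasi-likelihood or a two-part model is needed because a full gamma likelihood does not accept zeros.

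Use the same cost model for the ICER, so that the test and the ratio share one estimate. Drop the log t-test and its variance pre-check, or keep the log t-test only as a sensitivity analysis with a stated rule for zeros.

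This needs wording only: no new data, and model classes that section 10.6 already allows. The small downside is wider intervals, because skewed costs make the arithmetic mean less precise than the mean log.

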7.9 Data Collection from CMS and State Medicaid Agencies

Medicare and Medicaid claims data from CMS and state Medicaid agencies will be used to assess health care utilization, costs, and medications among participants covered by either Medicare or Medicaid. Claims made in the period of 12 months prior to surgery (acute pain) or return of results (chronic pain, depression) through 6 months following those events will be collected. See Section 9 and the MOP for additional details. Schedule of Activities and Timeframe for Collection of Endpoints

Table 8. Data collection schedule

Data collection schedule, method of data collection, and timing

Outcome	Data source/instrument	Baseline	10 d ± 3 d	1 mo. ± 7 d	3 mo. ± 14 d	6 mo. ± 14 d
Pain Assessments						
Pain intensity	PROMIS Pain intensity scales	AP, CP	AP	AP, CP	AP, CP*	AP, CP
Pain intensity	PROMIS Numeric Rating Scale - Pain Intensity (NPRS)	AP	AP*	AP	AP	AP
Daily opioid dose & type of opioid use	Average daily mg morphine equivalents (MED) since discharge use of opioids: tramadol/ codeine vs others		AP*	AP		
Opioid use disorder	PROMIS - Prescription pain medication misuse subscale	AP, CP			AP, CP	AP, CP
Mobility	PROMIS mobility	AP	AP	AP	AP	AP
Depression Assessments						
Depressive state	PROMIS Emotional Distress - Depression 8b survey	CP, D		CP, D	CP, D*	CP, D
Depressive state	Patient Health Questionnaire-8 depression scale	D			D	D
Participant Medications						
Assessment of prescriptions	Custom survey/EHR	AP, CP, D	AP		CP, D	
Assessment of filled prescriptions	Medicaid and Medicare billing records for 12 months prior to time 0 through 6 months after time 0			AP, CP, D		

Adherence	Voils Medication Adherence		D		D	D	D
SSRI AE Survey	Custom survey		D		D	D	D
Opioid side effect survey	Adapted medication side effect survey (SPACE)		AP, CP	AP	AP, CP	AP, CP	AP, CP
Opioid persistence	Custom survey						AP
Participant Actions							
Interaction with provider	Participant visits				CP, D		
Interaction with test result	Custom survey						AP, CP, D
Quality of life and well being							
Past Medical History	Participant visits/custom survey		AP, CP, D				
Well-being	PROMIS43/PROMIS Peds37		AP, CP, D		AP, CP, D	AP, CP, D	AP, CP, D
Healthcare Utilization and Costs							
Medicare/Medicaid billing records	Medicaid and Medicare billing records for 12 months prior to time 0 through 6 months after time 0				AP, CP, D		
LoS	LoS for index admission			AP			

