9.2 Data Collection

Data for this specialized analysis will come from these sources:

1. Participant report of healthcare utilization (e.g. emergency department, urgent care, office) for all participants, these will focus on high-cost items and/or items that are expected to be sensitive to the intervention
2. Medicare claims data for Medicare enrollees
3. Medicaid claims data for Medicaid enrollees

Participant reported visits: Participant reported assessment for health care utilization is previously described in section 7.3.

Medicare claims data: For Medicare enrollees in fee-for-service (FFS) plans or Medicare Advantage, clinical groups will ascertain Medicare claims data (Part A-D) directly from the Centers for Medicare and Medicaid Services (CMS).

Medicaid claims data: For Medicaid enrollees, clinical groups will ascertain claims data from their states' Medicaid agencies directly.

To ensure full adjudication, requests to Medicare/Medicaid for claims data will be timed to occur between 6-12 months after the end of the 6-months follow-up of the last enrolled patient. Claims data will also be requested for one year before trial enrollment up to 6 months thereafter.

The procedure for obtaining claims data will require a database linkage step – mapping the participant study ID to the Medicare/Medicaid identifiers. The data linkage will rely on social security number (SSN) or Medicare ID and date of birth (DoB), which can be collected in two possible ways:

1. Both SSN and/or Medicare ID and DoB are collected as part of the trial by the recruiting site
2. One or both variables are extracted from the medical record of the participating health center by a healthcare data security officer or the local equivalent, on behalf of the study team

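### The claims-based cost comparison names no adjustment for prior-year cost, although claims for that year are already requested

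*Combined protocol and SAP*

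**What the plan says.** Section 10.6 (Cost Effectiveness) has two relevant parts.

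- **Healthcare costs.** The test is limited to enrollees in Medicaid or in Medicare fee-for-service and is stated as follows: "log-transformed overall expenditures (between index visit and 6 months follow-up) will be compared using a 2-sample t-test between the study arms". A second route follows: "Alternatively, cost comparisons will be made using appropriate regression models such as generalized linear models". No covariates are listed, and no rule says when the second route replaces the first.
- **Cost utility.** "Cost and quality adjusted life year (QALY) estimates, adjusted for clustering within site and baseline utility for QALYs", are to come from regression models. Then "The Incremental cost-effectiveness ratio (ICER) will be calculated from costs and QALY", with bootstrap intervals.

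Two sections describe the earlier claims. Section 7.9 refers to "Claims made in the period of 12 months prior to surgery (acute pain) or return of results (chronic pain, depression) through 6 months" afterwards, and Table 8 likewise counts back 12 months from time zero. Section 9.2 says: "Claims data will also be requested for one year before trial enrollment up to 6 months thereafter".

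Section 9.1 expects at least 60% of the study population to have claims and gives the payer's reimbursement decision as the purpose of the economic work. Section 10.6 leaves further detail to a study SAP, which Section 10.2 describes as a separate document and which is not part of the text reviewed here.

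**The concern.** Prior-year cost is the baseline value of the cost outcome. The plan requests the data for it but names it in no cost model. In the same sentence the cost-utility model does name a baseline term, but only for QALYs. The cost comparison has no stated power, and its claims-based form is limited to participants with linked claims, so precision is likely to be what limits it. Two things are at stake: precision that could be had from data already requested, and a chance difference between arms in prior cost, part of which stays in the estimated cost difference.

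**Working it through.** **Which analysis uses which baseline**

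| Analysis in Section 10.6 | Cost data | Baseline term named for cost |
|---|---|---|
| Log-cost t-test | Claims, index visit to 6 months | None |
| Alternative regression | Not stated | None |
| Cost-utility regression | Not restricted to claims | None (site clustering only; baseline utility for QALYs) |

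**Stated figure.** The documents give no SD, effect size, power or sample size for cost, so there is no cost figure to reproduce. Table 9 concerns the primary endpoints. I use only its chronic pain total, which does follow from its inputs: 134 / 0.30 = 446.7, so 447 per arm; 894 / 0.90 = 993.3, so 994.

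**Inputs**
- Two-sided alpha 0.05 (Section 10.2, for tests with no other level stated) and 1:1 allocation (Section 4.1).
- Share with claims 60% (Section 9.1).
- rho, the within-arm correlation of prior and follow-up log cost: *not in the documents*. Assumed range 0.3 to 0.6.

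**Formulas** (linear adjustment of an approximately normal log cost)
- Variance factor: 1 − rho².
- SE factor: √(1 − rho²).
- Equivalent sample-size gain: 1 / (1 − rho²).
- Power after adjustment, for a comparison with 80% power unadjusted: 1 − Φ(1.96 − 2.802/√(1 − rho²)), where 2.802 = 1.960 + 0.842.
- Shift in the unadjusted estimate, given an imbalance of k standard errors in prior cost: rho × k standard errors.
- Type I error given that imbalance: 1 − Φ((1.96 − rho·k)/√(1 − rho²)) + Φ((−1.96 − rho·k)/√(1 − rho²)).

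| rho (assumed) | Variance cut | SE factor | Sample-size gain | 80% power becomes | Type I error of unadjusted test at k = 1.96 |
|---|---|---|---|---|---|
| 0.3 | 9% | 0.954 | ×1.10 | 83.6% | 7.9% |
| 0.5 | 25% | 0.866 | ×1.33 | 89.9% | 12.9% |
| 0.6 | 36% | 0.800 | ×1.56 | 93.8% | 16.4% |

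Averaged over all possible imbalances, the type I error of the unadjusted test remains 5%. With no imbalance it is below 5% (4.0%, 2.4% and 1.4% for the three correlations). The last column therefore shows sensitivity to an unlucky allocation, not an inflated error rate for the plan.

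**Scale, chronic pain as an example.** 0.60 × 994 / 2 gives about 298 per arm with claims. The SE of a chance imbalance in standardised prior log cost is √(2/298) = 0.082 SD. The effect detectable with 80% power is 2.802 × 0.082 ≈ 0.229 SD of log cost unadjusted, and 0.219, 0.199 and 0.184 SD after adjustment at rho 0.3, 0.5 and 0.6.

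**The two prior-cost windows.** Section 7.9 counts back from surgery or return of results; Section 9.2 counts back from enrolment. Section 6.3 lets investigators withdraw acute pain participants who have no surgery within 12 months of enrolment, so surgery can fall up to a year after enrolment. A surgery-anchored prior year can then lie partly or largely after randomisation. In chronic pain and depression the overlap is shorter but still present: randomisation follows sample collection (Section 7.4), and time zero falls later, at return of results or one week after sample collection (Section 7.3).

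**The case against.** The strongest reply is that the plan leaves this open. The regression route neither fixes nor rules out covariates, and the detail is deferred to a separate SAP. That stands: a reader might infer that prior cost has been deliberately excluded, and the documents do not show this. They show that it is not named. The point survives because the same section names a baseline term for QALYs, and because cost covariates are best fixed before the claims are seen.

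The economic analyses are also exploratory, as the synopsis says, and no power is claimed for them. That stands too, and it limits the importance of the point.

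Four stronger readings are tempting, and the documents support none of them.

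- *The cost comparison is biased.* It is not: randomisation keeps it unbiased on average, and only rho times a chance imbalance stays in the estimate, not the whole of it.
- *The unadjusted t-test drives the ICER.* It does not. That test compares geometric means, and the ICER's cost term comes from the separate cost-utility regression. That regression also lacks prior cost, but it is not limited to claims holders. Sections 9.2 and 10.6 assign costs to other participants from self-reported use.
- *The variance figures apply to any cost model.* They describe linear adjustment of log cost. They need not hold for a generalized linear model of skewed cost, or for bootstrap intervals around an ICER.
- *Every Medicare or Medicaid participant will have a prior-cost value.* Section 9.1 allows for enrolment gaps and Section 9.2 depends on an identifier linkage. The t-test covers Medicare fee-for-service and Medicaid only, although Medicare Advantage claims are also sought.

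**Conclusion.** The point holds as a cheap gain in precision, not as an error that invalidates the cost analysis. The stated cost comparison makes no use of a baseline value that the study already plans to obtain, and the cost-utility model adjusts only the effect side for baseline. Under an assumed correlation of 0.3 to 0.6, linear adjustment would reduce the variance of the log-cost difference by 9% to 36%, equivalent to about 1.1 to 1.6 times as many participants. The size rests wholly on that assumed correlation. The benefit is confined to participants with linked claims; on the Section 9.1 figure, up to about 40% (100% − 60%) may have none. The covariate is a true baseline only if its window closes at randomisation, which Section 7.9 as written does not ensure.

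**What to change.** 1. **Section 10.6, Healthcare costs.** State that the claims-based comparison, among participants with linked claims, is a regression of follow-up cost on arm, cost in the 12 months ending at randomisation, months of claims coverage in that window, and the randomisation strata of Section 4.1. Fix the model form in advance so that it replaces the open choice between t-test and regression.
2. **Section 10.6, Cost utility.** Where the analysis is run in participants with claims, add the same prior-cost term to the cost model and take costs and QALYs from the same participants. Do not put a claims-only cost difference into an ICER whose QALYs come from everyone.
3. **Sections 7.9 and 9.2.** Reconcile the two windows. The extract should cover both the 12 months before randomisation and the 6 months after time zero, and the covariate should contain no post-randomisation cost.

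This needs no new visits or participants. It costs SAP and protocol wording, plus a check that the claims request spans both periods, and it should be settled before claims are analysed. For participants without claims there is no dependable substitute as the plan stands: Section 7.3 lists a baseline utilisation survey for chronic pain and depression, but Table 8 shows the visit items only at 1, 3 and 6 months.
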